At all office visits, subjects should be observed after study drug administration until judged clinically stable by the study personnel. If an anaphylactic reaction or other serious allergic reaction occurs, administration of study drug should be discontinued immediately and initiate appropriate therapy. When dosing at home subjects should be instructed to contact the site immediately with any signs or symptoms of a reaction. If subjects are unable to reach their study site or experience life-threatening symptoms, they will be instructed to call an emergency number or proceed to the nearest emergency room and then inform the site as soon as possible.

Subjects will be instructed to return all used and unused syringes, sharps containers and empty boxes at each visit for accountability.

Dose Escalation

At or after Week 12, if any subject experiences inadequate response (defined below), the subject may increase dose to open-label adalimumab 80 mg eow. If the subject has received open-label 80 mg eow therapy and continues to demonstrate inadequate response, they should be withdrawn from the study.

For the Purposes of Dose Escalation, Inadequate Response:

Crohn's disease activity index (CDAI) ≥ 200 and at least one of the following criteria is met: an increase of at least 1 mg/L in level of high-sensitivity C-reactive protein (hs-CRP) from Baseline or an hs-CRP ≥ 5 mg/L.

The hs-CRP results used to determine inadequate response should be the most recent available results. Assessment of inadequate response should include consideration by the Investigator to rule out symptoms caused by reasons other than Crohn's disease related inflammation. The most recent hs-CRP value should first be compared to the most recent CDAI from the previous visit. Then the most recent hs-CRP value should be assessed in relation to CDAI calculated at the current visit. Dose changes are to only occur in accordance with the eow dosing schedule.

For example:

Week 12 CDAI was 190 and the hs-CRP obtained at Week 12 visit was 7 mg/L. The subject returns 2 weeks later and the CDAI at Week 14 is 220. The hs-CRP obtained at Week 12 should first be assessed with the Week 12 CDAI to determine if the inadequate response criteria have been met; which in this case does not meet criteria for dose escalation. Then the hs-CRP obtained at Week 12 should be assessed with Week 14 CDAI, which does meet the criteria for dose escalation; because the latter assessment met the criteria, the subject is eligible for dose escalation.

Laboratory Tests

Blood samples will be obtained for the laboratory tests listed in [Table 3](#) at the visits described in [Table 1](#). Blood draws should be performed after all clinical assessments and questionnaires (CDAI, IBDQ), vital sign determinations are obtained and before study drug administration during a visit, whenever possible.

A certified central laboratory will be utilized to process and provide results for the clinical laboratory tests. All abnormal laboratory tests that are considered clinically significant by the investigator will be followed to a satisfactory resolution.

The central laboratory chosen for this study will provide instructions regarding the collection, processing and shipping of these samples.

Table 3. Clinical Laboratory Tests

Hematology	Clinical Chemistry	Urinalysis	Other	Pregnancy Test
Hematocrit	Blood Urea Nitrogen (BUN)	Specific gravity	hs-CRP	Serum HCG
Hemoglobin	Creatinine	Ketones	C. difficile toxin	Urine (testing to be performed locally by designated study personnel)
Red Blood Cell (RBC) count	Total bilirubin	pH	Fecal calprotectin	
White Blood Cell (WBC) count	Serum glutamic-pyruvic transaminase (SGPT/ALT)	Protein	Antinuclear antibody (ANA)	
Neutrophils	Serum glutamic-oxaloacetic transaminase (SGOT/AST)	Blood	Anti-double-stranded DNA (anti-dsDNA) – if ANA positive	
Bands	Alkaline phosphatase	Glucose	HBs Ag	
Lymphocytes	Sodium		HBs Ab	
Monocytes	Potassium		HBe Ag	
Basophils	Calcium		HBe Ab	
Eosinophils	Inorganic phosphorus		HBc Ab Total	
Platelet count (estimate not acceptable)	Uric acid		PCR DNA (if needed)	
	Cholesterol		Pharmacokinetic	
	Total protein		HACA	
	Glucose		Infliximab	
	Triglycerides		Pharmacogenetic (optional)	
	Albumin		mRNA (optional)	
			HCV	
			HIV (testing to be conducted at central lab)	
			QuantiFERON-TB	
			Gold In-Tube	

Hepatitis and HIV Testing

All subjects will be tested for the presence of the HBV at Screening. A positive result for the HBs Ag will be exclusionary. If HBc Ab test results are positive, polymerase chain reaction (PCR) DNA will be performed to exclude the HBV infection, any result that

meets or exceeds detection sensitivity will be exclusionary. If HBe Ag or HBe Ab are positive, the subject's eligibility is per investigator's discretion.

Anti-Hepatitis C antibody will be performed at Screening only. A positive result will be exclusionary.

Subjects will be tested for antibodies to HIV-1 at Screening. This testing is to be done at a central laboratory. A subject will not be eligible for study participation if confirmatory testing for anti-HIV-1 antibody is positive. AbbVie will not receive results from the testing and not be made aware of any positive result. If the subject had negative anti-HIV-1 test results from the central lab, these tests will not be required to be repeated if the results were obtained within 50 days of the re-screening visit provided that in the meanwhile nothing has changed in the patient's medical history or risk behaviors.

If the subject had negative HBV and Anti-Hepatitis C test results from the central lab, these tests will not be required to be repeated if the results were obtained within 35 days of the re-screening visit.

Pregnancy Tests

A serum pregnancy test will be performed at the Screening Visit on all female subjects of childbearing potential. At the Baseline Visit (Week 0) and Week 26/PD subjects of childbearing potential will have a urine pregnancy test performed locally by designated study personnel. If any urine pregnancy test is positive, a serum pregnancy test will be performed by the central laboratory. A lactating or pregnant female will not be eligible for participation or continuation in this study.

All women of childbearing potential will have a repeat urine pregnancy test at the final onsite Study Visit performed locally by designated study personnel.

Urinalysis

Urine samples will be obtained and sent to the central laboratory for the tests listed in [Table 3](#) at the visits described in [Table 1](#). Microscopic urinalysis will only be performed

d by the central laboratory if the dipstick urinalysis results are abnormal, where abnormal is defined as a ketone, protein, blood value greater than negative or glucose value of greater than a normal.

Other Laboratory Assessments

ANA/anti-dsDNA

Blood samples for antinuclear antibody (ANA) will be obtained per [Table 1](#). Anti-double-stranded DNA (anti-dsDNA) assessments will be performed if ANA is positive.

In the event that subject develops lupus-like symptoms during the study, an additional ANA sample will be obtained.

hs-CRP

Blood samples for hs-CRP will be obtained per [Table 1](#). The site will receive the notification from the central laboratory for the Screening Period. Results obtained during the Day -7 Screening visit (for a subject who started TB prophylaxis) will be used for entry criteria.

The hs-CRP results from Week 2 through Week 8 will remain blinded to Investigator, study site personnel and the subject. The AbbVie safety team will not be blinded to these results. Since investigators are blinded to hs-CRP, the SDP will notify the investigator of an elevated hs-CRP result (> 100 mg/L) and request follow-up.

Blood draws should be performed after all clinical assessments and questionnaires (including CDAI), vital sign determinations are obtained and before study drug administration during a visit.

Fecal Calprotectin

Fecal calprotectin will be performed for all subjects as indicated in [Table 1](#) and collection should be performed before study drug administration during a visit as much as possible.

If subjects are unable to provide a sample at the site visit, they will be sent home with a stool sample collection supplies and instructions to assist the subjects with the collection procedures.

The fecal calprotectin results will remain blinded to Investigator, study site personnel and the subject up to and including Week 8.

The central laboratory will be utilized to process and provide results for these laboratory tests.

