- u. Collection of Serious Adverse Events (SAEs) and protocol-related nonserious adverse events begins the day the subject signs the informed consent. Collection of AEs begins on Day -7 for subjects who initiate TB prophylaxis.
- v. Administration of drug should be performed after all assessments and examinations scheduled for that day have been completed as much as possible. Starting at or after Week 12 and if the subject qualifies for dose escalation (criteria defined in Section 5.3.1.1 and per investigator discretion), the subject may receive 80 mg of adalimumab eow.
- w. Dosing may occur onsite by appropriate site staff or the subject or their qualified designee can administer doses when not at the site.
- x. For damaged or replacement study drug, subject should stay on their dosing schedule established by the Baseline (Week 0) visit.
- y. Procedure should be performed if subject doses onsite, if subject doses at home these procedures are not required.

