Study drug will be administered to all subjects onsite by site medical staff during all the visits from Baseline (Week 0) through Week 24. No study drug will be administered at Week 26. Detailed instructions and training for the administration of adalimumab are provided in [Appendix E](#) and [Appendix F](#). Study drug kits are assigned by IRT following the subjects randomized treatment schedule. If the subject chooses to dose outside of the clinic at the visit weeks specified in [Table 1](#), adalimumab injections occurring during study visits will be performed at the visit by the subject or their designated family member, friend or Healthcare Professional under the supervision of trained medical personnel to reinforce proper aseptic SC injection technique. Subjects or a trained designated family member, friend or Healthcare Professional will perform the injections of adalimumab in the subject's home during the weeks they are not in for scheduled clinic visits.

When dosing onsite, each subject will have a Dosing Log or accountability form at Baseline (Week 0); this log must be filled out each time a dose is administered. In the dosing log, the date and time study drug is administered, and the dose administered will be recorded. Additionally, any discernible departure from the protocol regarding study

drug administration will be recorded on the source documents and on the appropriate drug accountability form.

Site medical staff or subjects, if dosing occurs at the subject's home, should administer study medication on the same day of the week. The dosing dates for all doses of study drug should be calculated from the Baseline (Week 0) Visit date. A ± 3 -day window is allowable for scheduled study dosing dates. For subjects who deviate from this dosing window, every effort should be made to bring the subject back to the original dosing schedule as soon as possible. For situations where bringing the subject back on the original dosing schedule will cause the dose to be out of the ± 3 day window, please contact the AbbVie SDP for additional instructions.

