6.0 Analysis Conventions

Definition of Baseline

The Baseline Visit date is the date when the first dose of study drug is received and referred to as Day 1 or Week 0. The baseline value for a variable is defined as the last non-missing value on or before the date of the first dose of study drug.

When analyzing laboratory parameters and vital signs on the Any Adalimumab analysis set, the Baseline Visit date is the date when the first dose of adalimumab is received and will be counted as Day 1 or Week 0. The baseline value for a laboratory or vital sign measurement is defined as the last non-missing value on or before the date of the first dose of adalimumab.

Definition of Final Observation

Final observation in the 4-week DB placebo controlled treatment period is defined as the last non-missing observation collected within 70 days following the last dose of study drug or the date subjects initiate adalimumab therapy not supplied in the context of Study M14-233 for subjects who discontinue the study before Week 6, and on or before the day of the first dose of study drug at Week 6 for subjects who continues the study.

Final observation in the DB/OL period for the Any Adalimumab set is defined as the last non-missing observation collected within 70 days following the last dose of study drug, or the date subjects initiate adalimumab therapy not supplied in the context of Study M14-233.

Definition of Rx Days (Days Relative to the First Dose of Study Drug)

Rx Days are calculated for each time point of interest and provide a quantitative measure of days between the event and Day 1 (which can be the day of the first dose of study drug or the day of the first dose of adalimumab, depending on the analysis). That is, the Rx Day is calculated as the event date minus Day 1 plus 1. The Rx Day will be a negative value when the time point of interest is prior to Day 1, and the Rx Day will be a positive

value when the time point of interest is after Day 1. By this calculation algorithm, the first dose day is Rx Day 1, while the day prior to the date of first dose is defined as Rx Day –1 (there is no Rx Day 0). Rx Days are used to map actual study visits to the protocol-specified study visits.

Definition of Analysis Windows

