Since subjects do not always adhere to the study visit schedule, the following rules will be applied to assign actual visits to protocol-specified visits including early termination visits. For each study visit mentioned in the protocol, a nominal or target day will be selected to represent the corresponding visit along with a window around the target day. Windows will be selected in a non-overlapping fashion so that a date collected on the CRF does not correspond to multiple visit windows. Moreover, windows will not discard any post-baseline measurement recorded on the CRF. If a subject had two or more actual visits in one visit window, the visit closest to the target will be used as the study visit for that window. If two visits are equidistant from the target, then the later visit will be used for reporting. For efficacy related analyses, if multiple measurements for a particular parameter are collected on the same day for the same subject, the average of those measurements will be used. For safety related analyses, if multiple measurements are made for a particular laboratory or vital sign parameter on the same day for the same subject, the average of the values will be used in the analyses. For summaries and listings of shift from baseline and potentially clinically significant values all values will be considered in the analyses.

Table 2. Visit Windows for Analysis of CDAI and Vital Sign

Scheduled Week	Nominal Day	Time Window (Rx Day A Range)
Week 0 DB	1 ^a	≤ 1
Week 2 DB	15	2 – 22
Week 4 DB	29	23 – 36
Week 6 DB	43	37 – 50
Week 8 DB	57	51 – 64 ^b
Week 10 OL	71	65 ^c – 78
Week 12 OL	85	79 – 92
Week 14 OL	99	93 – 106
Week 16 OL	113	107 – 120
Week 18 OL	127	121 – 134
Week 20 OL	141	135 – 148
Week 22 OL	155	149 – 162
Week 24 OL	169	163 – 176
Week 26 OL	183	177 – 190

Rx Day A = date of visit – date of first study drug injection in double-blind treatment period + 1

- a. Date of first study drug injection in double-blind treatment period.
- b. For Week 8 DB, visit window was from Rx Day 51 to Rx Day 64 or the date of the first injection in OL period (if applicable), whichever comes first.
- c. For Week 10 OL, visit window was from Rx Day 65 or the date of the first injection in OL period + 1 (if applicable), whichever comes first, to Rx Day 78.

Table 3. Visit Windows for Analysis of hs-CRP, Chemistry and Hematology

Scheduled Week	Nominal Day	Time Window (Rx Day A Range)
Week 0 DB	1 ^a	≤ 1
Week 2 DB	15	2 – 22
Week 4 DB	29	23 – 36
Week 6 DB	43	37 – 50

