Week 8 DB	57	51 – 71 ^b
Week 12 OL	85	72 ^c – 99
Week 16 OL	113	100 – 127
Week 20 OL	141	128 – 162
Week 26 OL	183	163 – 190

Rx Day A = date of visit – date of first study drug injection in double-blind treatment period + 1

- a. Date of first study drug injection in double-blind treatment period.
- b. For Week 8 DB, visit window was from Rx Day 51 to Rx Day 71 or the date of the first injection in OL period (if applicable), whichever comes first.
- c. For Week 12 OL, visit window was from Rx Day 72 or the date of the first injection in OL period + 1 (if applicable), whichever comes first, to Rx Day 99.

Table 4. Visit Windows for Analysis of Urinalysis

Scheduled Week	Nominal Day	Time Window (Rx Day A Range)
Week 0 DB	1 ^a	≤ 1
Week 4 DB	29	2 – 43
Week 8 DB	57	44 – 71 ^b
Week 12 OL	85	72 ^c – 112
Week 20 OL	141	113 – 161
Week 26 OL	183	162 – 190

Rx Day A = date of visit – date of first study drug injection in double-blind treatment period + 1

- a. Date of first study drug injection in double-blind treatment period.
- b. For Week 8 DB, visit window was from Rx Day 37 to Rx Day 71 or the date of the first injection in OL period (if applicable), whichever comes first.
- c. For Week 12 OL, visit window was from Rx Day 72 or the date of the first injection in OL period + 1 (if applicable), whichever comes first, to Rx Day 112.

Table 5. Visit Windows for Analysis of Fecal Calprotectin and IBDQ

Scheduled Week	Nominal Day	Time Window (Rx Day A Range)
Week 0 DB	1 ^a	≤ 1
Week 4 DB	29	2 – 43
Week 8 DB	57	44 – 71 ^b
Week 26 OL	183	72 ^c – 190

Rx Day A = date of visit – date of first study drug injection in double-blind treatment period + 1

- a. Date of first study drug injection in double-blind treatment period.
- b. Rx Day 71 or the date of the first injection in OL period (if applicable), whichever comes first.
- c. For Week 26 OL, visit window was from Rx Day 72 or the date of the first injection in OL period + 1 (if applicable), whichever comes first, to Rx Day 190.

Vital signs and laboratory measurements will also be presented on the Any Adalimumab set using the visit windows in the following tables.

Table 6. Visit Windows for Analysis of CDAI and Vital Sign (Any Adalimumab)

Visit Week	Nominal Day	Time Window (Rx Day B Range)
Week 0	1 ^a	≤ 1
Week 2	15	2 – 22
Week 4	29	23 – 36
Week 6	43	37 – 50
Week 8	57	51 – 64
Week 10	71	65 – 78
Week 12	85	79 – 92
Week 14	99	93 – 106
Week 16	113	107 – 120
Week 18	127	121 – 134
Week 20	141	135 – 148

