10.3 Secondary Efficacy Analyses

The Week 26 efficacy endpoint is proportion of subjects who achieve clinical remission at Week 26 (CDAI < 150) in subjects who achieved clinical response (decrease in CDAI ≥ 70 points from Baseline) at Week 8. The one sample Exact test will be performed by comparing it to the clinically meaningful remission rate of 30%, and the two-sided 95% CI will be provided.

Key secondary efficacy endpoints include:

- Proportion of subjects who achieve CDAI < 150 plus a reduction in hs-CRP of at least 50% from Baseline at Week 4.
- Proportion of subjects who achieve CDAI < 150 plus a reduction in hs-CRP of at least 50% from Baseline at Week 26 in subjects who achieved decrease in

CDAI \geq 70 points from Baseline plus at least 30% reduction in hs-CRP from Baseline at Week 8.

- Proportion of subjects who discontinue corticosteroid use and achieve clinical remission (CDAI $<$ 150) at Week 26 in subjects who were taking steroids at Baseline and who achieved clinical response (decrease in CDAI \geq 70 points from Baseline) at Week 8.
- Proportion of subjects who discontinue corticosteroid use and achieve CDAI $<$ 150 plus a reduction in hs-CRP of at least 50% from Baseline at Week 26 in subjects who were taking steroids at Baseline and who achieved decrease in CDAI \geq 70 points from Baseline plus a reduction in hs-CRP of at least 30% from Baseline at Week 8.
- Proportion of subjects who achieve clinical response (decrease in CDAI \geq 70 points from Baseline) at Week 4.
- Proportion of subjects who achieve decrease in CDAI \geq 70 points from Baseline plus a reduction in hs-CRP of at least 30% from Baseline at Week 4.
- Proportion of subjects who achieve CDAI $<$ 150 and hs-CRP $<$ 3 mg/L at Week 4.
- Proportion of subjects who achieve CDAI $<$ 150, hs-CRP $<$ 3 mg/L at Week 26 in subjects who achieved clinical response (decrease in CDAI \geq 70 points from Baseline) at Week 8.
- Proportion of subjects who achieve IBDQ remission (IBDQ \geq 170 points) at Week 4.
- Proportion of subjects who achieve IBDQ remission at Week 26 in subjects with clinical response (decrease in CDAI \geq 70 points from Baseline) at Week 8.
- Change from Baseline in fecal calprotectin level at Week 4.
- Proportion of subjects who achieve CDAI $<$ 150, hs-CRP $<$ 3 mg/L and fecal calprotectin $<$ 250 μ g/g at Week 4.

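### Home-collected stool and an uncapped SAP window let a placebo subject's Week 4 fecal calprotectin be measured after the first 160 mg of adalimumab

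*Protocol*

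**What the plan says.** Protocol 5.3.1.1 (Fecal Calprotectin) says that "collection should be performed before study drug administration during a visit as much as possible", and then: "If subjects are unable to provide a sample at the site visit, they will be sent home with a stool sample collection supplies". It gives no deadline for the home sample and no rule tying it to a visit. The same section has dosing at the visit: "Study drug will be administered to all subjects onsite by site medical staff during all the visits from Baseline (Week 0) through Week 24". Note v to Protocol Table 1 places the dose after the day's assessments, again with a qualifier: "Administration of drug should be performed after all assessments and examinations scheduled for that day have been completed as much as possible". Placebo-arm subjects receive their first adalimumab, 160 mg, at Week 4 (Protocol 5.1).

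SAP 6.0 defines Baseline by date, not time: "The baseline value for a variable is defined as the last non-missing value on or before the date of the first dose of study drug". The governing table is headed "Table 5. Visit Windows for Analysis of Fecal Calprotectin and IBDQ". It gives Week 0 as Rx Day 1 or earlier, Week 4 as Days 2–43 (target 29), Week 8 as Days 44–71 (target 57) and Week 26 as Days 72–190 (target 183). The Week 8 window closes early at the first open-label injection; the Week 4 window has no equivalent cut. SAP 6.0 also says that "windows will not discard any post-baseline measurement recorded on the CRF", and takes the visit closest to target when several fall in one window. The Rx Day definition in SAP 6.0 uses the event date, while the note to Table 5 uses the date of visit.

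Two key secondary endpoints in SAP 10.3 use the Week 4 stool: "Change from Baseline in fecal calprotectin level at Week 4", and the composite of CDAI < 150, hs-CRP < 3 mg/L and calprotectin < 250 µg/g.

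**The concern.** The randomized comparison with placebo ends when the placebo arm is given adalimumab at Week 4. The SAP respects that boundary elsewhere: SAP 11.2.1 ends the placebo-controlled adverse event period at the Week 4 dose, and SAP 10.3 runs the between-group analyses over time from Week 0 to Week 4 only.

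The CDAI and hs-CRP windows (SAP Tables 2 and 3) also lack a cut at the Week 4 injection. However, those measures are taken at the visit, and their Week 4 windows run only from Day 23 to 36. Calprotectin is the measure that may be collected after the visit, and its window runs a week longer. A subject who cannot produce stool at Week 4 is likely to be dosed and then collect at home. In the placebo arm that stool is post-adalimumab, yet it is analysed as placebo. At stake is dilution of two key secondary comparisons.

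**Working it through.** **Inputs.** Table 5 windows and targets, the closest-to-target rule and the two Rx Day definitions (SAP 6.0); ±3-day visit tolerance (Protocol Table 1, note b); placebo arm 160 mg at Week 4 and 80 mg at Week 6 (Protocol 5.1).

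**1. Reproducing the window.** The upper bound is the midpoint of the Week 4 and Week 8 targets: (29 + 57)/2 = 43. The lower bound is the day after the Baseline cut-off: 1 + 1 = 2. Both agree with Table 5. The window spans 43 − 2 + 1 = 42 days.

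**2. Post-adalimumab days still counted as Week 4 (placebo arm).** With the Week 4 injection on Day d, Days d + 1 to 43 qualify, which is 43 − d days.

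| Week 4 injection | Days counted as Week 4 after it | Share of the 42-day window |
|---|---|---|
| Day 26 | 43 − 26 = 17 | 40% |
| Day 29 | 43 − 29 = 14 | 33% |
| Day 32 | 43 − 32 = 11 | 26% |

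If the Week 6 visit falls on Day 40, the last 43 − 40 = 3 days also follow the 80 mg dose. These are the limits the SAP permits, not expected collection times. A pre-dose stool on the target day would displace a later one, but the subjects concerned are those who had none at the visit.

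**3. Effect on the difference.** Let f be the share of placebo Week 4 stools that are post-dose and g the share of the full drug effect they already show. The placebo mean moves toward the active mean by f × g × D, so the observed difference is D × (1 − f × g). The documents give neither f nor g. As an assumption only, f = 5–30% and g = 10–50% give a shrinkage of 0.05 × 0.10 = 0.5% to 0.30 × 0.50 = 15%.

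**4. Late Baseline stool, by dating rule.**
- *Collection (event) date.* A stool passed on Day 1 after the dose still counts as Baseline, because the rule uses dates. A stool from Day 2, 3, 5, 8 or 15 falls in Week 4. With stools on Days 3 and 29, Day 29 is the Week 4 value and Baseline is missing, so there is no change value and no Baseline-calprotectin subgroup (SAP 10.5). With Day 3 alone, Day 3 becomes the Week 4 value; it cannot enter the change analysis without a Baseline and can matter only in the composite. Protocol Table 1, as far as it is legible, lists no calprotectin stool before Baseline to fall back on.
- *Visit date.* The late stool is labelled Baseline although it follows the first dose. A home stool from Week 4 is labelled Week 4 whenever it was passed, so in the placebo arm it still follows 160 mg. Here even the Day 43 limit does not bind.

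**5. The cap.** If the Week 4 window ended on the injection date and stool were dated by collection, the days in step 2 would fall from 14 (11–17) to 0. Only same-day stools would remain to be separated by time. The cap does not recover a late Baseline stool.

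**The case against.** Collection before dosing is the default, and these subjects have active disease with CDAI 220–450, so failing to produce stool may be uncommon. The protocol does not state that a subject who cannot produce stool is dosed first; that is inferred from onsite dosing. Take-home and laboratory instructions outside these documents may set a deadline. A kit sent home would often come back within a day or two, when adalimumab may have changed calprotectin little. Any bias runs toward no difference, so it cannot manufacture a positive result. All of this limits the size. It does not remove the gap: nothing in the documents excludes a stool at the far edge of the window, and Table 5 shows that its authors knew how to cut a window at an injection.

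A reader might infer that a late Baseline stool routinely becomes the Week 4 result. The documents do not support that. Any stool nearer Day 29 displaces it, the change endpoint cannot use it without a Baseline, and on the visit-date reading it is not misfiled at all. In the composite it matters only for a subject with no nearer stool who also meets the CDAI and hs-CRP criteria, and only if the misfiled value is below 250 µg/g; otherwise the outcome is the same as non-responder imputation.

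A reader might also attach a precision loss. An assumed 10–30% of subjects without Baseline would widen the confidence interval by 1/√0.9 = 1.05 to 1/√0.7 = 1.20. No rate in the documents supports such a figure.

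**Conclusion.** The point holds for the placebo arm at Week 4. The protocol permits post-dose home stool without a deadline, and Table 5 accepts it as Week 4 for up to 14 days (11–17) after the first 160 mg of adalimumab. If adalimumab lowers calprotectin, the Week 4 difference shrinks in two key secondary endpoints. The amount depends on a home-collection rate and an early drug effect that the documents do not give, so the 0.5–15% range is illustration only.

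The Baseline problem is secondary and conditional. If stool is dated by collection, a sample from Day 2 or later leaves Baseline missing, and it serves as the Week 4 value only when no stool lies nearer Day 29. The SAP's two date definitions need reconciling either way. It would go too far to infer harm to the primary endpoint: its CDAI result uses no stool sample, and only its subgroup analyses by Baseline calprotectin are touched.

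**What to change.** 1. **Protocol 5.3.1.1.** Hand out the stool kit at the preceding visit (for example, Week 2 for the Week 4 sample), so that the subject brings stool passed shortly before the visit. It then precedes that visit's dose, and dosing itself is unchanged.
2. **SAP Table 5, calprotectin only, both arms.** End the Week 4 window at Rx Day 43 or the date of the Week 4 injection, whichever comes first, and start the Week 8 window the day after, so that no value is discarded. Use collection time to separate same-day stools passed before and after the dose. Give IBDQ its own table, since Table 5 governs both.
3. **SAP 6.0.** State that Rx Day for stool uses the collection date. The cap needs this: under the visit date, a post-dose home stool would still be labelled Week 4.

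**Cost.** A site instruction, different kit timing, a recorded collection date and time, and short SAP edits before database lock; no new visit. Some Week 4 stools passed after dosing become missing for Week 4. Those subjects are non-responders in the composite, and LOCF cannot fill the change value because Baseline is not carried forward. A late Baseline stool could also be left as the only one in the shortened window. Earlier kit hand-out should keep both rare.
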